6.11.2. Pharmacokinetic Assessments

Testing of PK samples will be carried out by the central PK laboratory using validated methods. Logistic considerations may dictate a deviation from the specified time point; therefore, a window is permitted around each sampling time point, as shown in [Table 4](#): sampling times up to and including 1 hour postdose have a window of ± 5 min and subsequent time points have a window of ± 10 min. At Treatment Period visits, study drug and replacement glucocorticoid and mineralocorticoid (if applicable) doses are expected to be administered at approximately the same time. At Treatment Period visits, actual dosing times of nevanimibe HCl, glucocorticoids, and mineralocorticoids (if applicable) must be recorded using the eDiary; and actual times of PK sampling must be recorded on the eCRF.

Table 4: Pharmacokinetic Sampling Time Points

Visit	Sampling Time Points (Morning Dose Only)
T1, T2, T3, T4, T5/EoT	0 hours (trough, within 30 min predose); and 1 hour (± 5 min), 2 hours (± 10 min), 3 hours (± 10 min) and 4 hours (± 10 min) postdose

Specific collection and shipment procedures for PK samples are provided in the Laboratory Manual.

PK parameters will be computed using non-compartmental methods. The PK parameters outlined in Table 5 will be estimated for nevanimibe and its major metabolite(s) as data permit and as appropriate. PK parameters may also be estimated for replacement glucocorticoids and/or mineralocorticoids as appropriate.

Table 5: Pharmacokinetic Parameters

C_{last}	last quantifiable drug concentration determined directly from individual concentration-time data
C_{max}	maximum observed drug concentration determined directly from individual concentration-time data
C_{max}/D	dose-normalized C_{max} , calculated as the ratio of C_{max} to dose
T_{max}	observed time to reach maximum drug concentration
AUC_{0-4}	area under the concentration-time curve from time zero to 4 h after dosing, calculated using the linear-up/log-down trapezoidal rule
AUC_{0-4}/D	dose-normalized AUC_{0-4} , calculated as the ratio of AUC_{0-4} to dose
AUC_{0-t}	area under the concentration-time curve from time zero to the time of the last quantified concentration, calculated using the linear-up/log-down trapezoidal rule
λ_z	terminal phase rate constant, estimated by linear regression through the terminal phase of the log concentration-time profile
$t_{1/2}$	terminal phase half-life, calculated as: $t_{1/2} = \frac{\ln(2)}{\lambda_z}$

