$AUC_{0-\infty}$	area under the concentration-time curve from time zero to infinity (first dose only), calculated as $AUC_{0-4} + C_{last}/\lambda_z$
$AUC_{\%extrap}$	percentage of $AUC_{0-\infty}$ extrapolated, represented as $(1 - AUC_{0-t}/AUC_{0-\infty}) \times 100$
CL/F	oral clearance calculated as: dose/ $AUC_{0-\infty}$ (Day 1 only)

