7.8 Evaluation of Pharmacokinetic Variables

Pharmacokinetic parameters (C_{last} , C_{max} , C_{max}/D , T_{max} , AUC_{0-4} , AUC_{0-4}/D , AUC_{0-t} , λ_z , $t_{1/2}$, $AUC_{0-\infty}$, $AUC_{\%extrap}$, CL/F) for nevanimibe and its major metabolite(s) will be computed as data permit and as appropriate

using non-compartmental methods employing WinNonlin® Phoenix version 6.3 or later (Pharsight Corp., Mountain View, CA). PK parameters may also be estimated for replacement glucocorticoids and/or mineralocorticoids as appropriate.

The pharmacokinetic analyses will be described in detail in a separate PK Analysis Plan by Certara USA, Inc. (Princeton, New Jersey, USA) as it will be conducted separately from the analyses described in this document.

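### Protocol Table 5 adds the extrapolated tail to AUC0-4 instead of AUC0-t, so AUC0-∞, percent extrapolated and CL/F are exact only when the last quantifiable sample is at 4 h

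*Protocol*

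**What the plan says.** All the relevant definitions are in Table 5 of Protocol section 6.11.2.

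- **Clast:** "last quantifiable drug concentration determined directly from individual concentration-time data". No clock time is attached to it.
- **AUC0-4:** "area under the concentration-time curve from time zero to 4 h after dosing, calculated using the linear-up/log-down trapezoidal rule". The upper limit is fixed.
- **AUC0-t:** "area under the concentration-time curve from time zero to the time of the last quantified concentration". The upper limit moves with the data.
- **AUC0-∞:** the "area under the concentration-time curve from time zero to infinity (first dose only"), "calculated as $AUC_{0-4} + C_{last}/\lambda_z".
- **Percent extrapolated:** one minus the ratio of AUC0-t to AUC0-∞, times 100.
- **CL/F:** dose divided by AUC0-∞, on Day 1.

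Table 4 in the same section places the last sample at 4 h with a ±10 min window, and the text requires actual sampling times to be recorded. SAP section 7.8 lists the same parameters without formulas, says that they "will be computed as data permit and as appropriate", and leaves the detail to a separate PK Analysis Plan, which is not among the documents.

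**The concern.** Clast/λz is the area under a log-linear tail that starts at tlast. It completes the curve only if the first term also stops at tlast. Table 5 pairs it with an area that stops at 4 h. The row for percent extrapolated, by contrast, treats AUC0-t as the observed part, so the two rows agree only when tlast is 4 h.

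The documents allow tlast to differ from 4 h. The window permits a last sample between 3 h 50 min and 4 h 10 min, and a 4 h sample may be missing or below the assay limit. Neither document says how AUC0-4 is then obtained.

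Determining the PK parameters of nevanimibe and its metabolites is a secondary objective. AUC0-∞, percent extrapolated and CL/F are all listed outputs and all inherit the formula.

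**Working it through.** The plan gives no figure to reproduce. The check is algebra, followed by an illustration of size.

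**Algebra**

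- Correct value: AUC0-t + Clast/λz.
- Table 5 value: AUC0-4 + Clast/λz.
- Error = Table 5 − correct = AUC0-4 − AUC0-t.

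Three cases follow.

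1. tlast = 4 h: AUC0-4 = AUC0-t, so the error is zero.
2. tlast < 4 h: if AUC0-4 is carried to 4 h along the log-linear tail, the error is +(Clast/λz) × (1 − exp(−λz(4 − tlast))). Only the piece from tlast to 4 h is counted twice. If AUC0-4 is simply stopped at tlast, the error is zero.
3. tlast > 4 h: the error is minus the area from 4 h to tlast, which appears in neither term.

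**Inputs for size**

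The 4 h last sample and the ±10 min window come from Table 4. The documents give no half-life, absorption rate, assay limit or proportion of profiles ending before 4 h. Assumed: a one-compartment oral curve, C(t) = ka/(ka − λz) × (exp(−λz t) − exp(−ka t)), with ka = 2/h and half-lives of 0.5, 1, 2, 4 and 8 h.

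**Worked example: half-life 2 h, tlast = 3 h**

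- λz = ln 2/2 = 0.3466/h, C(3) = 0.4247 and Clast/λz = 1.225.
- AUC0-t (0 to 3 h) = 1.653, so the correct AUC0-∞ = 1.653 + 1.225 = 2.878.
- Segment from 3 to 4 h = 1.225 × (1 − exp(−0.3466)) = 0.359.
- Table 5 value = 2.878 + 0.359 = 3.237.
- AUC0-∞ error = 3.237/2.878 − 1 = +12.5%. CL/F error = 2.878/3.237 − 1 = −11.1%.
- Percent extrapolated: correct 1 − 1.653/2.878 = 42.6%; Table 5 1 − 1.653/3.237 = 48.9%.

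**Error in AUC0-∞ across the assumed range**

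| Half-life (h) | tlast 2 h | 3 h | 3 h 50 min | 4 h | 4 h 10 min |
|---|---|---|---|---|---|
| 0.5 | +13.8% | +3.2% | +0.3% | 0 | −0.2% |
| 1 | +27.1% | +9.4% | +1.2% | 0 | −1.0% |
| 2 | +29.7% | +12.5% | +1.8% | 0 | −1.7% |
| 4 | +22.5% | +10.3% | +1.6% | 0 | −1.6% |
| 8 | +13.9% | +6.7% | +1.1% | 0 | −1.1% |

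The matching CL/F errors are −3.1% to −11.1% at tlast = 3 h and −12.1% to −22.9% at 2 h. If a below-limit 4 h value is instead set to zero and joined by a straight line, the AUC0-∞ error at tlast = 3 h is +3.0% to +7.4%.

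**The case against.** The strongest reply is that the design makes the error negligible. The last sample is scheduled at 4 h. If it is quantifiable and on time, AUC0-4 and AUC0-t are the same number, and within the window they differ little. Nothing in the documents suggests that many Day 1 profiles end early. Where one does, λz rests on at most three post-dose points and may not be estimable, and the plan reports parameters only where the data allow. The unseen PK Analysis Plan may already carry the right formula. The whole point also turns on one subscript in one row.

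Most of this stands and limits the size of the point. It does not make the formula right. Table 5 distinguishes the subscripts 4 and t in neighbouring rows, including the next one, so the row as it stands is inconsistent with its own table.

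Three stronger readings are tempting, and the documents do not support them.

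- **That AUC0-∞ is always too high when the last sample is off 4 h, or that the whole tail is counted twice.** Only the segment from tlast to 4 h can be counted twice. That requires tlast before 4 h and an AUC0-4 carried on to 4 h, a step that neither document specifies. After 4 h the sign reverses.
- **That the error at tlast = 3 h reaches 16% to 18%.** Such figures arise from fixing a profile, say concentrations of 0.8, 1.2 and 1.0 at 1, 2 and 3 h, and then imposing half-lives of 1 or 2 h. The two declining points give λz = ln(1.2) = 0.182/h, a half-life of about 3.8 h, and an error of about 11%.
- **That the plan has no safeguard against heavy extrapolation.** Sampling to 4 h does leave a large tail in the assumed model even with the right formula: 30% of AUC0-∞ at a half-life of 2 h and 55% at 4 h. But percent extrapolated is a listed output, reporting is conditional on the data, and the detail is deferred to a plan that cannot be inspected. The absence of a limit cannot be shown, and any particular cut-off would be a preference.

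**Conclusion.** The AUC0-∞ formula in Table 5 is wrong as written and disagrees with the percent-extrapolated row beneath it; CL/F inherits the error. The algebra needs no assumption. The sizes rest on the one-compartment curve described above and, for tlast before 4 h, on AUC0-4 being carried to 4 h.

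On that basis the error is nil for an on-time quantifiable 4 h sample and under 2% in either direction within the window. It is material only for profiles whose last quantifiable sample is a full hour or more early. How many there will be cannot be judged from the documents.

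The consequence for the trial is small. AUC0-∞ and CL/F are descriptive and confined to the first dose. Protocol section 9.7.1 names Cmax, Tmax and AUC0-4 as the PK endpoints and relates Cmax and AUC0-4 to 17-OHP. The criterion for a positive study depends on 17-OHP response alone. This is a correction worth making, not a threat to the study's conclusions.

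**What to change.** In Protocol Table 5, replace AUC0-4 with AUC0-t in the AUC0-∞ row, giving AUC0-∞ = AUC0-t + Clast/λz. This matches the percent-extrapolated row and removes the error for any tlast. Confirm that the PK Analysis Plan uses the same definition.

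It would also help if that plan said how AUC0-4 is obtained when the 4 h value is missing, below the assay limit or off nominal time, since AUC0-4 is itself a named endpoint. A limit on the extrapolated share is not needed for this correction.

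The cost is one symbol in one table and a check of one other document. There are no new samples, and no change to visits or to any other analysis.

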6.11.3. Pharmacodynamic Assessments

The relationship between C_{\max} , T_{\max} , AUC_{0-4} and other PK parameters with efficacy assessments will be explored as appropriate and as data allow.

6.11.4. Blood Sample Collection, Storage and Shipping

Sample collection, storage and shipment procedures for clinical laboratory samples are provided in the Laboratory Manual.

7. STUDY ACTIVITIES

Subjects do not need to be fasting prior to any of the study visits. For each study visit, the first hormone sample collection that is obtained at the study site should be done between 6-10 AM (06:00-10:00), as close to 8 AM (08:00) as practicable.

The day *before* each study visit, subjects should pay particular attention to noting the actual time of their last doses of glucocorticoid and study drug (if applicable). On the morning of study visits, including Visit T5/EoT, subjects should wait to take their morning doses of study drug (if applicable), glucocorticoid, and mineralocorticoid (if applicable) until directed by personnel at the study site.

Study visit designations (S1, B1, T1, F1, etc.) are shown in the detailed schedule of study assessments provided in [Appendix 1](#). Please note that below and in Appendix 1, the assigned Study Day is the first day of the corresponding Study Week. For example, the Day 85 visit occurs following 12 full weeks of dosing with study drug, at the beginning of Week 13.

7.1. Screening Period

During the Screening Period, the eligibility of the subjects is assessed. The Screening Period may last from approximately 2-14 weeks, depending on whether the subject is in Cohort 1 or Cohort 2, and on the number of maintenance glucocorticoid dose adjustments required for Cohort 2 subjects. The Screening Period concludes with the start of the Baseline Period.

Prior to the Screening visit, appropriate study site personnel should:

- Remind the subjects that on the morning of the Screening visit, they should wait to take their morning doses of glucocorticoid and mineralocorticoid (if applicable) until directed by site personnel at the study site.
- Remind the subjects to bring their glucocorticoid and mineralocorticoid (if applicable) containers to each study visit.

7.1.1. Visit S1

The Screening visit can be conducted approximately 2-14 weeks prior to the Baseline visit. The date of screening is considered to be the date that the first study-related screening assessment is performed. At screening, appropriate study site personnel should:

- Obtain and document informed consent from the subject prior to any study procedures being performed.
- Assign a study-specific subject number.
- Obtain and record medical history, demographic data and prior and current medications. If the subject is a premenopausal woman, obtain the start date of her last menstrual period.
- Record any AEs that occurred after informed consent was signed.
- Record the date and time of the subject's last dose of glucocorticoid prior to the visit.
- Record vital signs, height and weight.
- Perform a complete PE.

- Obtain a 12-lead ECG.
- Review all assessable inclusion and exclusion criteria.
- Within 30 minutes prior to administration of morning replacement glucocorticoid and mineralocorticoid (if applicable) doses, collect blood samples for hematology, chemistry, PT, aPTT, INR, HBsAg, HCV, HIV, 17-OHP, P, cortisol, and (for female subjects of childbearing potential only) a serum pregnancy test.
 - For each study visit, the first hormone sample collection that is obtained at the study site should be done between 6-10 AM (06:00-10:00), as close to 8 AM (08:00) as practicable.
 - Hormones should not be collected if the subject already took their replacement glucocorticoid and/or mineralocorticoid dose that morning; instead, the sample collection should be rescheduled for the next day or as soon as is feasible.
 - Note: The serum 17-OHP may be repeated one time at the Investigator's discretion if there is reason to suspect the results are inaccurate.
- Collect a urine sample for urinalysis and urine drug screen.
- Ask the subject to self-administer their morning replacement glucocorticoid and mineralocorticoid (if applicable) doses. Record the time of glucocorticoid and mineralocorticoid (if applicable) administration.
- If the subject is a premenopausal woman, instruct the subject to make note of the first day of each of her menstrual periods during the study.
- Remind the subjects that on the morning of their next study visit, they should wait to take their morning dose of glucocorticoid and mineralocorticoid (if applicable) until directed by site personnel at the study site.
- Remind the subjects to bring their glucocorticoid and mineralocorticoid (if applicable) containers to their next study visit.

7.1.2. After Visit S1

Within approximately 2 weeks after Visit S1, appropriate study site personnel should:

- Review all assessable inclusion and exclusion criteria.
- Review serum 17-OHP results (see Appendix 2).
- Contact the subject via telephone to:
 - Record AEs and update medications. If the subject is a premenopausal woman, obtain the start date of her last menstrual period.
 - If serum 17-OHP is $\geq 4x$ ULN (Cohort 1), schedule the subject for the Baseline visit, Visit B1.
 - If serum 17-OHP is $< 4x$ ULN (Cohort 2), assess the subject's maintenance glucocorticoid replacement dose in equivalent mg of hydrocortisone/m² body surface area (see Appendix 3).

- If ≥ 12 mg/m², reduce the dose by the equivalent of approximately 5 mg hydrocortisone or 1 mg prednisone or prednisolone, and schedule the subject to return for Visit S2 approximately 2-4 weeks after the dose change.
- If < 12 mg/m², discuss the case with the Medical Monitor; screen-fail the subject if no further glucocorticoid dose reduction is possible.
- Remind the subjects that on the morning of their next study visit, they should wait to take their morning dose of glucocorticoid and mineralocorticoid (if applicable) replacement until directed by site personnel at the study site.
- Remind the subjects to bring their glucocorticoid and mineralocorticoid (if applicable) containers to their next study visit.

7.1.3. Visit S2 (Cohort 2 Subjects Only)

Subjects in Cohort 1 should skip Visit S2 and proceed to the Baseline Visit (Visit B1).

Subjects in Cohort 2 should undergo Visit S2 at least 2 weeks after the last decrease in their maintenance glucocorticoid dose.

At the S2 visit, appropriate study site personnel should:

- Record AEs and update medications. If the subject is a premenopausal woman, obtain the start date of her last menstrual period.
- Record the date and time of the subject's last dose of glucocorticoid prior to the visit.
- Record vital signs and weight.
- Within 30 minutes prior to administration of morning replacement glucocorticoid and mineralocorticoid (if applicable) doses, collect blood samples for 17-OHP, P, and cortisol.
 - For each study visit, the first hormone sample collection that is obtained at the study site should be done between 6-10 AM (06:00-10:00), as close to 8 AM (08:00) as practicable.
 - Hormones should not be collected if the subject already took their replacement glucocorticoid and/or mineralocorticoid dose that morning; instead, the sample collection should be rescheduled for the next day or as soon as is feasible.
- For female subjects of childbearing potential only, collect a urine sample and perform a urine pregnancy test.
- Ask the subject to self-administer their morning replacement glucocorticoid and mineralocorticoid (if applicable) doses. Record the time of glucocorticoid and mineralocorticoid (if applicable) administration.
- Schedule the next study visit (Visit B1) to occur at least 4 weeks after the subject's last maintenance glucocorticoid dose change.
- Remind the subjects that on the morning of their next visit, they should wait to take their morning dose of glucocorticoid and mineralocorticoid (if applicable) until directed by site personnel at the study site.
- Remind the subjects to bring their glucocorticoid and mineralocorticoid (if applicable) containers to their next study visit.

7.1.4. After Visit S2 (Cohort 2 Subjects Only)

Within approximately 2 weeks after Visit S2, prior to Visit B1, appropriate study site personnel should review serum 17-OHP results for Cohort 2 subjects (see Appendix 2):

- If serum 17-OHP is $\geq 4x$ ULN, the subject should return for the Baseline visit, Visit B1, as scheduled.
- If serum 17-OHP is $< 4x$ ULN, assess the subject's maintenance glucocorticoid replacement dose in equivalent mg of hydrocortisone/m² body surface area (see Appendix 3) and discuss the case with the Medical Monitor.
 - If ≥ 12 mg/m², with agreement of the Medical Monitor, it may be possible to further reduce the dose by the equivalent of approximately 5 mg hydrocortisone or 1 mg prednisone or prednisolone. The subject should then return for an Unscheduled visit approximately 2-4 weeks after the dose change (i.e., when the Investigator assesses that the subject's hormone levels have stabilized) to assess 17-OHP levels. Further management should be discussed and agreed with the Medical Monitor.
 - If < 12 mg/m², discuss the case with the Medical Monitor; screen-fail the subject if no further glucocorticoid dose reduction is possible.

7.2. Baseline Period

Subjects who meet all assessable inclusion and exclusion criteria, whose last 17-OHP obtained during the Screening Period was $\geq 4x$ ULN and last maintenance glucocorticoid dose change occurred at least 4 weeks prior, may enter the Baseline Period.

7.2.1. Visit B1 (Day -14; Week -2)

Prior to Visit B1, the Investigator should review whether the subject continues to be eligible for the study. If not, the subject should be screen-failed from the study. Please note that the Screening serum cortisol level result does not need to be available for the subject to proceed with Visit B1.

At Visit B1, appropriate study site personnel should:

- Record AEs and update medications.
- Record the date and time of the subject's last dose of glucocorticoid prior to the visit.
- Record vital signs and weight.
- Within 30 minutes prior to administration of morning replacement glucocorticoid and mineralocorticoid (if applicable) doses, collect blood samples for hormones (17-OHP, P, cortisol, A4, ACTH, total testosterone, and 11-ketotestosterone), and collect saliva samples for 17-OHP, P, and cortisol.
 - For each study visit, the first hormone sample collection that is obtained at the study site should be done between 6-10 AM (06:00-10:00), as close to 8 AM (08:00) as practicable.
 - Hormones should not be collected if the subject already took their replacement glucocorticoid and/or mineralocorticoid dose that morning; instead, the sample collection should be rescheduled for the next day or as soon as is feasible.

- For female subjects of childbearing potential only, collect a urine sample and perform a urine pregnancy test.
- Instruct the subject on the use of the eDiary for recording glucocorticoid, mineralocorticoid, and/or study drug doses. If needed, provision a device for accessing the eDiary.
- If the subject is a premenopausal woman, instruct her on the use of the eDiary for recording the start date of her last menstrual period, and ask her to record the start date of her last menstrual period using the eDiary.
- Ask the subject to self-administer their morning replacement glucocorticoid and mineralocorticoid (if applicable) doses.
- Ask the subject to record the time of glucocorticoid and mineralocorticoid (if applicable) administration using the eDiary.
- Remind the subjects to collect a salivary 17-OHP profile within approximately one week prior to the next study visit (Visit T1).
- Schedule the next study visit (Visit T1).
- Remind the subjects to record the actual time of their doses of glucocorticoid and mineralocorticoid (if applicable), particularly those taken on the day prior to their next visit, using the eDiary. If the subject is a premenopausal woman, also remind her to record the start date of her menstrual periods.
- Remind the subjects that on the morning of their next visit, they should wait to take their morning doses of glucocorticoid and mineralocorticoid (if applicable) until directed by site personnel at the study site.

7.2.2. After Visit B1

Within 2 weeks after Visit B1, prior to Visit T1, review serum 17-OHP results (see Appendix 2):

- If 17-OHP is $\geq 4x$ ULN:
 - If the subject met criteria for Cohort 1 based on the S1 serum 17-OHP, the subject should return for the Enrollment visit, Visit T1, as scheduled.
 - If the subject met criteria for Cohort 2 based on the S1 serum 17-OHP, assess stability of 17-OHP.
 - For the purposes of this study, “stable” serum 17-OHP levels following a glucocorticoid dose reduction are defined as the most recent two 17-OHP levels prior to enrollment being within 30% of each other (calculated as $100 \times (1 - (\text{smaller value}/\text{larger value}))$).
 - If 17-OHP levels are stable, the subject should return for the Enrollment visit, Visit T1, as scheduled.
 - If 17-OHP levels are not stable, discuss the case with the Medical Monitor, and consider obtaining a repeat serum 17-OHP level(s). Once the repeat 17-OHP levels are $\geq 4x$ ULN and meet stability criteria, the subject may proceed to the Enrollment visit, Visit T1.

- If 17-OHP is $< 4x$ ULN:
 - If the subject met criteria for Cohort 2 based on the S1 serum 17-OHP, assess the subject's maintenance glucocorticoid replacement dose in equivalent mg of hydrocortisone/m² body surface area (see Appendix 3) and discuss the case with the Medical Monitor.
 - If ≥ 12 mg/m², with agreement of the Medical Monitor, it may be possible to reduce the dose by the equivalent of approximately 5 mg hydrocortisone or 1 mg prednisone or prednisolone. The subject should then return for an Unscheduled visit at least 2 weeks after the dose change to assess 17-OHP levels. Further management should be discussed and agreed with the Medical Monitor.
 - If < 12 mg/m², discuss the case with the Medical Monitor.
 - In the unlikely event that a subject in Cohort 1 (based on the S1 serum 17-OHP), has 17-OHP $< 4x$ ULN, discuss the case with the Medical Monitor.

